## 7. Investigational Procedures

### 7.1 Design Overview

The Implantation with the Cochlear Nucleus® CI532 Implant - Early Experience Study will be conducted as a multi-center, prospective, single-arm clinical study, evaluating the safety and functionality of the Cochlear Nucleus CI532 cochlear implant in up to 50 subjects who meet current cochlear implant indications. A single-subject repeated-measures analysis will be employed whereby subjects will act as their own control. A single-subject research design is appropriate since it accommodates the heterogeneity that characterizes hearing-impaired populations. Blinding procedures are not appropriate for this trial design, as it is not possible to conceal the presence, or absence, of a cochlear implant from device recipients and/or clinical investigators.

### 7.2 Description of Test Measures

#### 7.2.1 Clinical Audiological Testing

Subjects will undergo a standard battery of audiological tests. Audiological data will be gathered pre-operatively, at Initial Activation (IA) and at 3-months post IA.

The clinical data gathered for this study will include:

- 1) Tympanometry, both ears.
- 2) Frequency-specific thresholds at standard audiometric frequencies for both ears.
  - a) Air conduction: 125, 250, 500, 750, 1000, 2000, 3000, 4000, and 8000 Hz
  - b) Bone conduction: 250, 500, 1000, 2000, 3000 and 4000 Hz
- 3) Aided speech recognition in quiet: AzBio sentences (Spahr et al., 2012) presented at 60 dBA in the sound field for the unilateral listening ear.
  - a) Sentence testing in quiet will only be conducted in subjects aged 12 years and older
- 4) Aided speech recognition in noise: AzBio sentences (Spahr et al., 2012) using speech weighted noise presented at 65 dBA with a +5 dB signal to noise ratio spatially separated, speech 0 degrees azimuth and noise 90 degrees towards the implanted ear.
  - a) Sentence testing in noise will only be conducted in subjects aged 12 years and older.

Note: The contralateral ear will be plugged/muffed for all audiological testing.

---

CONFIDENTIAL

March 31, 2016

CAM-CL-027\_PRT

Rev. 1

Page 11 of 21

## 7.2.2 Device Fitting

Mapping will be conducted using standard clinical procedures using Custom Sound default program settings for the Nucleus 6 sound processor.

## 7.3 Preoperative Procedures

### 7.3.1 Visit 1

A baseline evaluation will be conducted to measure the subject's preoperative, best aided, unilateral listening performance pre-surgery. The following audiological testing will be completed:

- 1) Tympanometry, both ears.
- 2) Frequency-specific thresholds at standard audiometric frequencies for both ears.
  - a) Air conduction: 125, 250, 500, 750, 1000, 2000, 3000, 4000, and 8000 Hz
  - b) Bone conduction: 250, 500, 1000, 2000, 3000 and 4000 Hz
- 3) Aided speech recognition in quiet: AzBio sentences (Spahr et al., 2012) presented at 60 dBA in the sound field for the unilateral listening ear.
  - a) Only to be collected on subjects aged 12 years and older.
- 4) Aided speech recognition in noise: AzBio sentences (Spahr et al., 2012) using speech weighted noise presented at 65 dBA with a +5 dB signal to noise ratio spatially separated, speech 0 degrees azimuth and noise 90 degrees towards the implanted ear for the unilateral listening ear.
  - a) Only to be collected on subjects aged 12 years and older.

## 7.4 Intraoperative Procedures

### 7.4.1 Visit 2

There are no modifications to the standard surgical procedure for this study.

All surgeons will be required to complete a surgical questionnaire for each implanted subject. Intraoperative measures (impedance and NRT) are optional.

Additionally, intraoperative imaging (plain film x-ray) is recommended but not required, consistent with the Cochlear Nucleus CI532 Surgeons Guide.

## 7.5 Postoperative Procedures

### 7.5.1 Visit 3

At the initial activation appointment, the following procedures will be completed:

---

CONFIDENTIAL

March 31, 2016

CAM-CL-027\_PRT

Rev. 1

Page 12 of 21

Cochlear

- 1) Tympanometry, both ears.
- 2) Frequency-specific thresholds at standard audiometric frequencies for both ears.
  - a) Air conduction: 125, 250, 500, 750, 1000, 2000, 3000, 4000, and 8000 Hz
  - b) Bone conduction: 250, 500, 1000, 2000, 3000 and 4000 Hz
- 3) The initial activation will be performed according to standard clinical procedures using Custom Sound and the default programming settings for the Nucleus 6 sound processor.
  - a) Impedances and NRT are to be measured.
  - b) An anonymous .cdx file will be provided to the study sponsor.
- 4) Audiologist Questionnaire will be completed for each subject.

#### 7.5.2 Visit 4

At 3 months postactivation, the following procedures will be completed:

- 1) Tympanometry, both ears.
- 2) Frequency-specific thresholds at standard audiometric frequencies for both ears.
  - a) Air conduction: 125, 250, 500, 750, 1000, 2000, 3000, 4000, and 8000 Hz
  - b) Bone conduction: 250, 500, 1000, 2000, 3000 and 4000 Hz
- 3) Aided speech recognition in quiet: AzBio sentences (Spahr et al., 2012) presented at 60 dBA in the sound field for the unilateral listening ear.
  - a) Only to be collected on subjects aged 12 years and older.
- 4) Aided speech recognition in noise: AzBio sentences (Spahr et al., 2012) using speech weighted noise presented at 65 dBA with a +5 dB signal to noise ratio spatially separated, speech 0 degrees azimuth and noise 90 degrees towards the implanted ear for the unilateral listening ear.
  - a) Only to be collected on subjects aged 12 years and older.
- 5) Mapping will be performed according to standard clinical procedures using Custom Sound and the default programming settings for the Nucleus 6 sound processor.
  - a) Impedances and NRT are to be measured.
  - b) An anonymous .cdx file will be provided to the study sponsor.

---

CONFIDENTIAL

March 31, 2016

CAM-CL-027\_PRT

Rev. 1

Page 13 of 21

## 7.6 Summary of Data Collection Visits

	Visit 1	Visit 2	Visit 3	Visit 4
Test	Baseline	Surgery	Initial Activation	3 Mos Post Activation
Informed Consent	X			
Tympanometry	X		X	X
Audiometric	X		X	X
AzBio Quiet	X*			X*
AzBio Noise	X*			X*
Surgical Questionnaire		X		
Intraoperative Testing		X (optional)		
Imaging		X (optional)		
Audiological Questionnaire			X	
Device Programming (.cdx)			X	X

\*Note for subjects aged 12 years and older.

## 8. Adverse Events

An adverse event (AE) is any undesirable clinical or medical occurrence associated with the use of the device, procedure, or participation in the study, which does not result in serious injury or illness related to the surgical procedure or the device.

A serious adverse event (SAE) is any untoward medical occurrence that

- results in death
- is life-threatening

---

CONFIDENTIAL

March 31, 2016

CAM-CL-027\_PRT

Rev. 1

Page 14 of 21

- requires inpatient hospitalization or prolongation of existing hospitalization
- results in persistent or significant disability/incapacity
- requires medical or surgical intervention to prevent life-threatening illness or injury or permanent impairment to a body structure or a body function
- leads to fetal distress, death, or congenital abnormality or birth defect
- is a medically important event or reaction

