## **8.1 Assessment and Reporting of Adverse Events**

To monitor subject safety throughout this study, any procedure or device related adverse events will be recorded. Information on all adverse events will be maintained by event type. The investigator will complete an Adverse Event form if any adverse event is reported or observed for a subject during this study, even if the event was acknowledged as a risk factor in the Informed Consent form.

Adverse device effects refer to any undesirable clinical or medical occurrence associated with use of the device or participation in the study. Any/all adverse device effects are to be recorded via the Adverse Event form. Adverse device effects will be reported if observed, even if they were acknowledged as risk factors in the Informed Consent form.

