## **8.2 Unanticipated Adverse Device Effects**

Unanticipated adverse device effects refer to any event not identified above that represents a “serious adverse effect on health or safety or any life-threatening problem or death caused by, or associated with, a device if that effect, problem or death was not previously identified in nature, severity, or degree of incidence in the investigational plan or application, or any other unanticipated serious problem associated with a device that relates to the rights, safety, or welfare of subjects.” [FDA 21 CFR 812.3(s)]

Investigators are to inform their respective Institutional Review Boards (IRBs) and Cochlear Americas immediately if an unanticipated adverse device effect is suspected (no more than 10 working days after the investigator learns of the effect). If the case is determined to be an unanticipated adverse device effect, the investigator will fill out an “Unanticipated Adverse Device Effect Form.” Cochlear Americas will report the results of an evaluation of the unanticipated adverse device effect to all reviewing IRBs and investigators within 10 working days after first receiving notice of the event.

---

CONFIDENTIAL

March 31, 2016

CAM-CL-027\_PRT

Rev. 1

Page 15 of 21

Cochlear

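### Sections 8 and 8.1 make association with the device, procedure or participation a condition for recording a non-serious event, and give serious events no recording route of their own, so events judged unassociated need not reach the safety dataset

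*Protocol*

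**What the plan says.** Protocol Section 7.1 describes a single-arm, multi-center study "evaluating the safety and functionality of the Cochlear Nucleus CI532 cochlear implant" in up to 50 subjects and states that "Blinding procedures are not appropriate for this trial design". Section 10.1 makes all consented subjects the population for safety evaluation.

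Section 8 defines an adverse event as "any undesirable clinical or medical occurrence associated with the use of the device, procedure, or participation in the study", with the further limit "which does not result in serious injury or illness related to the surgical procedure or the device". The serious-event definition in the same section has no such condition. It opens "A serious adverse event (SAE) is any untoward medical occurrence that" and lists the qualifying outcomes.

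Section 8.1 gives the recording rule: "any procedure or device related adverse events will be recorded". It adds that information on all adverse events is kept by event type, and that "The investigator will complete an Adverse Event form if any adverse event is reported or observed for a subject during this study". It also asks for the form for every adverse device effect, defined by association with use of the device or with participation. Section 8.2 requires the IRB and the sponsor to be told "immediately if an unanticipated adverse device effect is suspected".

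Neither document contains a relatedness scale, an instruction to record first and judge relatedness later, or an independent adjudicator. The SAP does not mention adverse events.

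**The concern.** Relatedness is normally a judgement made about an event that is already on a form. Here it helps decide whether there is a form at all. The two possible errors are then treated differently. An event wrongly called related is in the dataset and can be re-judged. An event wrongly called unrelated need not be in the dataset, so the sponsor may have nothing to re-judge.

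This matters because the study has one arm. The absolute count of events is the safety result, and it depends wholly on what is recorded. With up to 15 sites and at most 50 subjects, most sites will contribute few subjects. Differences between sites in what they regard as associated, or a cluster of events that each site dismissed separately, can be seen only if the events are collected centrally.

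**Working it through.** The plan states no expected event rate, safety margin or safety hypothesis, so there is no figure to reproduce. The check is to follow each kind of event through Sections 8, 8.1 and 8.2.

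| Event | Adverse event under Section 8? | Route to a form or report |
|---|---|---|
| Non-serious, judged associated | Yes | Adverse Event form (8.1) |
| Non-serious, judged unassociated | No | None stated |
| Serious injury or illness, related to the device | No, excluded by the second limit in the definition; it is an SAE | Adverse Event form through the device-effect sentence in 8.1; 8.2 if a suspected unanticipated effect |
| Serious injury or illness, related to the procedure only | No, same exclusion; it is an SAE | None stated, unless treated as a device effect or a suspected unanticipated effect; the device-effect sentence does not name the procedure |
| Serious, judged unassociated | No; it is an SAE | None stated |

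**Do the broader sentences in 8.1 rescue rows two and five?** The sentence on keeping information on all adverse events and the form-completion sentence both use the term adverse event, which Section 8 has already restricted. On a consistent reading they add nothing for an unassociated event. If they were meant to cover every occurrence, they conflict with the Section 8 definition and with the first recording rule in 8.1. Either way the text needs reconciling.

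**Does monitoring rescue them?** Section 13 opens source data to monitoring, audit and inspection, and Section 19 has the monitor compare the CRFs with source. An event left off under the protocol's own definition is not a discrepancy between the two, so the monitor need not query it.

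**Hypothetical illustration.** The rates below are assumptions and come from neither document. Only N = 50 does, and it is a ceiling. Let p be the true proportion of subjects with a device- or procedure-caused event, and q the share of those left off because they are attributed elsewhere.

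- Expected recorded cases = N × p × (1 − q)
- Chance that none is recorded = (1 − p(1 − q))^N

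| p | q | Expected cases | Chance of none |
|---|---|---|---|
| 10% | 0 | 50 × 0.10 = 5.0 | 0.90^50 = 0.5% |
| 10% | 25% | 50 × 0.075 = 3.75 | 0.925^50 = 2.0% |
| 10% | 50% | 50 × 0.05 = 2.5 | 0.95^50 = 7.7% |
| 5% | 0 | 50 × 0.05 = 2.5 | 0.95^50 = 7.7% |
| 5% | 25% | 50 × 0.0375 = 1.88 | 0.9625^50 = 14.8% |
| 5% | 50% | 50 × 0.025 = 1.25 | 0.975^50 = 28.2% |

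The table shows how the mechanism would work. It is not an estimate for this trial.

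**The case against.** The strongest reply has five parts.

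- **The wording is not exclusive.** Section 8.1 never says that nothing else may be recorded, and two of its sentences sound inclusive. This stands as far as ambiguity goes: a site that reads generously may record everything. It does not remove the filter, for the reason given above.
- **Association is weaker than causation.** The regulatory definition quoted in 8.2 treats the two as different, so an event close in time to surgery might qualify without a causal verdict. No passage says who judges association; that the site does so is a fair inference, because the investigator completes the form. This part stands, but 8.1 uses the narrower idea of relatedness, and the choice is left open.
- **There are other routes.** Suspicion alone triggers 8.2, source data are open to inspection, and the withdrawal form in Section 9.2 would show an event that ended participation. A reader might infer that misattributed events disappear before anyone can see them. The documents do not support that: the events may sit in source records. What can be said is that they need not reach the sponsor's dataset.
- **The direction is not proven.** A reader might infer that the safety result is biased low. Sites may also attribute unrelated events to the implant, which raises the count, and there is no between-arm comparison for unblinded judgement to distort. Undercounting is a risk built into the rule, not a demonstrated result.
- **The stakes are modest.** The implant is commercially available, is used within approved indications with no change to standard surgery, and safety carries no endpoint or hypothesis. That lowers the priority. It does not square with a stated aim of evaluating safety in all consented subjects.

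The Adverse Event form is not among the documents, so it cannot be said that relatedness goes unassessed in writing. The form may already have that field.

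**Conclusion.** The point holds in a limited form. As written, a non-serious event judged unassociated with the device, procedure or participation needs no form. An SAE has no recording route of its own; it reaches the form only as a device effect, or is reported as a suspected unanticipated one. This follows from a stated rule and is not just missing detail. The recorded count may be too low, by an amount that the documents do not allow one to estimate.

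The conclusion assumes that sites apply the Section 8 definition consistently wherever the term appears. It does not support the stronger claims that events are recorded only after an unblinded causal verdict, or that the safety result is known to be biased. The efficacy endpoints and sample size are unaffected.

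**What to change.** Reconcile Sections 8 and 8.1:

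1. In Section 8, define an adverse event as any untoward medical occurrence in a consented subject from consent to Visit 4, whether or not it is considered related. Remove both the association condition and the seriousness exclusion from the definition.
2. In 8.1, state that all adverse events, including SAEs, are recorded on the Adverse Event form.
3. Capture seriousness and relationship (device / procedure / neither) as separate classifications made after recording, if the form does not already do this.
4. In the SAP, report both all events and related events.

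The cost is protocol wording, at most two fields on an existing form, and some extra forms for unrelated events in at most 50 subjects followed to 3 months post-activation. The change does not remove site judgement about relatedness, since no adjudicator is added. It keeps the events on record so that the judgement can be reviewed.

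If data collection has already ended under the present wording, the report should say that the counts may omit events judged unassociated.

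### The AE definition shuts out serious events and no rule records SAEs, so a serious, anticipated event attributed to surgery alone has no explicit recording rule

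*Protocol*

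**What the plan says.** - **Protocol Section 8, AE.** The scope is broad, covering occurrences "associated with the use of the device, procedure, or participation in the study". It is then cut back to an occurrence "which does not result in serious injury or illness related to the surgical procedure or the device".
- **Protocol Section 8, SAE.** A separate definition begins "A serious adverse event (SAE) is any untoward medical occurrence that" and lists the seriousness criteria. It does not present an SAE as a kind of AE, and no later section uses the term.
- **Protocol Section 8.1, AE recording.** The section opens with the aim that "any procedure or device related adverse events will be recorded". The form rule is: "The investigator will complete an Adverse Event form if any adverse event is reported or observed for a subject during this study", including events already named as risks in the consent form.
- **Protocol Section 8.1, adverse device effects.** These are occurrences "associated with use of the device or participation in the study". All of them go on the Adverse Event form, with no severity limit and even when they were foreseen.
- **Protocol Section 8.2.** Investigators must tell the IRB and the sponsor "immediately if an unanticipated adverse device effect is suspected". The rule is confined to effects not previously identified.
- **Safety aim.** Section 7.1 describes the study as "evaluating the safety and functionality of the Cochlear Nucleus CI532 cochlear implant". Section 10.1 makes all consented subjects the ITT population for safety. The SAP contains no safety analysis.

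**The concern.** An AE definition normally contains the serious events as a subset. Here a clause in the definition takes serious surgery- or device-related harm out of it, and the form is then made to depend on the narrowed term. The SAE definition could have repaired this, but nothing follows from it: the protocol gives no form, timeline or tabulation for SAEs. This is a written rule with its boundary in the wrong place, not a detail left for a manual.

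A site that applies the definitions as written could leave a foreseeable but serious surgical complication off the form, and another site could record it. The safety tabulation would then depend on how each site read Section 8, and a low count of serious procedural events could not be taken at face value.

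**Working it through.** The documents state no figure on this point, so there is nothing to reproduce. The check is to take each kind of event through the three recording rules. Here 'serious' means resulting in serious injury or illness, the test used in the AE exclusion.

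| Event | AE rule (8 with 8.1) | Adverse device effect rule (8.1) | Unanticipated effect rule (8.2) |
|---|---|---|---|
| Non-serious, procedure- or device-related | Recorded | Recorded if linked to the device or to participation | Not applicable |
| Serious, device-associated, unanticipated | Excluded by definition | Recorded | Reported |
| Serious, device-associated, anticipated | Excluded by definition | Recorded | Not covered |
| Serious, anticipated, attributed to the procedure alone | Excluded by definition | Procedure not named | Not covered |

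Only the last row has no explicit route. Three readings bear on it.

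1. Section 8 lists device, procedure and participation as three separate items. The device-effect sentence in Section 8.1 keeps the first and third and drops the second. Section 7.4.1 says that the surgery is unmodified standard practice, so a site could reasonably regard a purely surgical harm as arising from neither device use nor study participation.
2. The Section 8.1 statement that procedure-related adverse events are recorded uses the defined term. Read strictly, it carries the exclusion with it.
3. The exclusion and the SAE criteria do not match. A prolonged hospital stay, for example, meets an SAE criterion but need not be a serious injury or illness, so it might still count as an AE. The two definitions therefore do not divide events cleanly into serious and non-serious.

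**Scale, by assumption only.** The documents give no rate for such events. Let p be the rate per subject, taken as 2% to 5%. Let n be 25 (the minimum to be recruited and implanted, Section 10.2) or 50 (the ceiling). The chance of at least one event is 1 − (1 − p)^n.

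- n = 25: 1 − 0.98^25 = 0.40; 1 − 0.95^25 = 0.72.
- n = 50: 1 − 0.98^50 = 0.64; 1 − 0.95^50 = 0.92.

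Expected counts are n × p: 0.5 to 1.25 with 25 subjects, and 1.0 to 2.5 with 50. These figures describe how often such an event might occur. They do not describe how often it would go unrecorded.

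**The case against.** The strongest reply is that no sensible site would read the text this way. Section 8 sets out a non-serious and a serious tier, Section 8.1 follows directly under a title about reporting adverse events, and a serious adverse event is in ordinary language an adverse event. Section 8.1 names procedure-related events. Section 9.2 uses AE generically when it lists reasons for discontinuation. Surgery is Visit 2, so a surgical complication can be read as associated with participation and would reach the form as an adverse device effect. Section 7.4.1 also requires a surgical questionnaire for every implanted subject.

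Much of this stands. It shows that the sponsor meant to capture procedural events, and it confines the gap to the last row of the table. It does not remove the exclusion, which is explicit and names the surgical procedure. It also does not supply a rule for SAEs. The questionnaire's contents are not described and nothing links it to the safety evaluation, so it can be neither relied on nor dismissed.

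A reader might infer something stronger: that no rule sends serious events to a form, and that the safety evaluation would miss its most important events. The documents do not support that. The device-effect rule captures serious device-associated events, foreseen or not, and Section 8.2 adds prompt reporting of unanticipated ones.

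**Conclusion.** The point holds in a limited form. On a literal reading, a serious, anticipated event attributed to the surgical procedure alone has no explicit recording rule. That conflicts with the intent of Section 8.1 and with the stated safety aim. The conclusion rests on the text alone and needs no event rate.

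The size of the effect on the safety results cannot be established from the documents. The probabilities above depend on assumed rates, and the higher pair also depends on reaching the 50-subject ceiling. It would be tempting to conclude that a report of no serious events is worthless, or to attach a confidence bound to a zero count. Either step assumes that every site adopts the literal reading every time, and the plan proposes no such inference and has no safety hypothesis. The primary speech-perception endpoints are unaffected. The correction should still be made, because it is cheap and removes a real ambiguity in safety capture.

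**What to change.** 1. In Protocol Section 8, delete the clause that excludes events resulting in serious injury or illness, so that SAEs become a subset of AEs.
2. In Section 8.1, state that every SAE, anticipated or not and whether related to the procedure or to the device, is recorded on the Adverse Event form and identified as serious. With this in place the device-effect definition need not be widened to include the procedure.
3. In Section 10.1 and the SAP, tabulate serious and non-serious events separately in the ITT population. That population includes consented subjects who are discontinued because an alternative device was implanted (Section 9.2).

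The cost is a short amendment and possibly a slightly higher reported event count. No added visits are needed. The Adverse Event form is not among the documents, so it may already have a seriousness field. The SAP is dated January 2018 and is largely in the past tense. If recording has already ended, the study report should state how sites handled serious procedure-related events.
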